Cognitive-Behavioral Therapy Skills Questionnaire (CBTSQ) is a 16-item scale consisting of two factors, Behavioral Activation and Cognitive Restructuring. The scale shows construct validity, appears sensitive to change among patients undergoing CBT treatment, and predicts reduction in depressive symptoms.(76)

Adherence with Antidepressant Medications: Team members have extensive experience using VA pharmacy data to assess adherence. We will construct medication possession ratios for antidepressants prescribed for the 3 months following enrollment and for 3-6 months following enrollment. In addition to pharmacy data, *The 8-item Morisky Medical Adherence Scale (MMAS)* will also be used to assess adherence and may be particularly helpful if patients receive some antidepressant medication fills outside of the VA. The MMAS-8 has been shown to be reliable (Cronbach's alpha = .83) and to be significantly correlated with the validated 4-item MMAS (Pearson correlation: 0.64, p<.05) (Moriskey et al., 2008).

Receipt of VA and non-VA Traditional In-Person Psychotherapy: We will review enrolled patients' VA medical record notes to determine their receipt of any traditional in-person psychotherapy and their completion of 8 in-person psychotherapy visits within 12 and 24 weeks following enrollment. We will also assess whether the Veteran received psychotherapy that was depression focused and evidence-based, assessing the presence of key phrases in notes that denote CBT, ACT, or IPT treatment. We will also determine non-VA psychotherapy use, using the Cornell Services Index, as patients may have started non-VA psychotherapy after enrollment. Finally, we will construct variables that indicate if the Veteran received any in-person psychotherapy (y/n), completed an adequate trial of any psychotherapy (y/n), received any evidence-based VA psychotherapy (y/n), and completed a trial of evidence-based VA psychotherapy (y/n).

Generalized Anxiety Disorder 7 item scale (GAD-7). The GAD-7 total score ranges from 0 to 21, with "cut scores" for mild, moderate and severe anxiety. Although originally developed for generalized anxiety disorder symptoms, the GAD-7 has good operating characteristics for detection and severity ratings of panic disorder and social anxiety disorder.(117)

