We have attempted to keep the burden of study assessments within reason, deliberately choosing some shorter measures of important constructs, if possible. (For example, we use the GAD-7 rather than the BAI for measurement of anxiety because of its shorter length.) The estimated times for study assessments is approximately 50-60 minutes, based on published questionnaire administration times and the use of the general rule of 5 closed-ended questions or 2 open-ended questions per minute.

The Interpersonal Support Evaluation List (ISEL) will only be administered at baseline and several covariates will be assessed using chart and administrative data, reducing patient burden.

Study Measures for Patient Completion	Screening	Baseline	12 weeks	24 weeks
Screening Measures				
Patient Health Questionnaire (PHQ-9)	X			
Computer Literacy (study specific questions)	X			
Primary Outcome Measures				
Inventory of Depression Symptoms – Self Report (IDS-SR)		X	X	X
Veterans RAND 12-Item Health Survey (VR-12)		X	X	X
Quality of Life Enjoyment and Satisfaction Questionnaire		X	X	X
Recovery Assessment Scale (RAS)		X	X	X
Secondary Outcome Measures*/ Many also Mediators				
Depression Coping Self-Efficacy Scale (DCSES)		X	X	X
Cognitive-Behavioral Therapy Skills Questionnaire (CBTSQ)		X	X	X
Adherence with Antidepressant Medications (MPR* and BMQ)		X	X	X
Receipt of Traditional In-Person Psychotherapy		X	X	X
State Hope Scale (SHS)		X	X	X
Patient Activation Measure		X	X	X
Internalized Stigma of Mental Illness (ISMI)		X	X	X
Working Alliance with Peer Specialist (study specific questions)			X	X
Generalized Anxiety Disorder -7 (GAD-7)		X	X	X
Beck Scale for Suicidal Ideation (BSS)		X	X	X
Other Covariates				
Demographics		X		
Alcohol use (AUDIT-C)		X	X	X
Primary care provider mental health activity*		X		
Concurrent health services use (VA administrative data* and CSI)		X	X	X
Mental health and substance use comorbidities*		X		
General medical burden*		X		
Baseline social support (ISEL)		X		
Distance to VA facility (calculated by staff)*		X		

*calculated by staff, no burden on patient

E.11 Study Analyses

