Effects over time: We will next compare the effects of the PS-cCBT intervention versus EUC over time. This second set of analyses will use linear mixed-effects model with outcomes at all three assessment times as the response variable. The mixed-effects model will include patient as random intercepts to take into account the correlation of data within person over time. The model will allow the full use of all observed data despite missing outcomes at one or two assessment times and will give unbiased estimates as long as the missingness does not depend on the unobserved missing data (missing at random).

Using this model, we will be able to estimate the time-averaged effect of the intervention if the response to the intervention is immediate and lasting, or compare the rates of changes in the outcomes between the two groups if the outcomes show different trends between the study groups. Whether we compare the time-averaged effects or the rates between two groups, we will be guided by careful graphical exploration of the longitudinal data over time between the two groups. For example, if we find scores from IDS-SR to slowly decrease over time in the intervention group, but to slightly increase in the enhanced usual care group, we will model this by including a continuous time indicator (e.g., month since randomization) and a time by intervention group term in the model. The coefficient from the interaction term will estimate the difference in rates of change in outcomes between the two study groups.

E.11.c Secondary Outcomes: Analyses of secondary outcome of Depression Coping Skills and antidepressant medication adherence will proceed as outlined above for the primary outcome variables. For analyses of receipt of VA and non-VA traditional in-person psychotherapy, we will compare the percent

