initiating traditional psychotherapy between 12 to 24 weeks in patients in PS-cCBT versus EUC who have continued significant depressive symptoms at 12 weeks, defined as IDS-SR >16. The likelihood of initiation of traditional psychotherapy by 24 weeks will be compared using logistic regression model. As patients in need of continuing treatment at 12 weeks from the two groups are likely to differ, the model will be adjusted for variables that show meaningful differences between groups at 12 weeks. Although completion of a traditional therapy trial will be of interest, our primary interest here will be to see whether PS-cCBT increases the likelihood that Veterans would initiate a traditional therapy.

E.11.d Secondary Aim: Mediation of Intervention Effects on Symptoms, Functioning, QoL: We will examine whether any improvements in the primary outcomes of depressive symptoms, quality of life, functional status, or recovery focus are mediated through increased medication adherence or increased depression coping skills. To test whether a variable might be a mediator, we will first test the associations between the intervention and the mediator, and then the mediator and the outcome of interest using bivariate analyses. A variable will be considered a potential mediator if the variable is associated with both the intervention and the outcome in these analyses (i.e., as determined by a significance level of $P < .10$), and changes in the mediating variable occur prior to changes in outcomes.

Finally, for primary outcomes, such depressive symptoms at 24 weeks, we will additionally include the change in depression coping score from baseline to 24 weeks and/or change in antidepressant adherence from baseline to 24 weeks. If, as hypothesized, the intervention's effects on the primary outcomes are mediated through changes in depression coping or increased antidepressant adherence, the variance in 24 week symptoms explained by the intervention group will be less once the depression coping scores and antidepressant adherence are taken into account. We will also consider change in depression coping score from baseline to 12 weeks and/or antidepressant adherence at 12 weeks as potential mediators as the early effect of intervention on these variables may have affected the 24 week outcome.

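### The longitudinal analysis chooses between a time-averaged effect and a difference in slopes after outcomes are plotted by arm, and gives no treatment term for the time average although baseline is in the response

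*Combined protocol and SAP*

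**What the plan says.** E.11.b makes the 24-week comparison primary, by regression with the baseline value as covariate, and plans the same regression at week 12. Under Effects over time it adds a longitudinal analysis: "This second set of analyses will use linear mixed-effects model with outcomes at all three assessment times as the response variable". E.1 and the E.10 schedule put the assessments at baseline, 12 and 24 weeks, so baseline is one of the three responses. The model has a patient random intercept.

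Two comparisons are then offered. The first is conditional: "we will be able to estimate the time-averaged effect of the intervention if the response to the intervention is immediate and lasting". The second is a difference in rates of change, if the arms show different trends. Between them, "we will be guided by careful graphical exploration of the longitudinal data over time between the two groups". As an illustration, the plan would use continuous time and a time-by-group term if it found IDS-SR scores "to slowly decrease over time in the intervention group, but to slightly increase in the enhanced usual care group". No term is given for the time average.

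E.13 expects more than 90% power if 0.4 SD is the time-averaged difference, without saying which visits are averaged. E.11.c extends the approach: "Analyses of secondary outcome of Depression Coping Skills and antidepressant medication adherence will proceed as outlined above for the primary outcome variables".

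**The concern.** There are two gaps. First, the estimand is picked from outcome data shown by arm. A p-value from a comparison selected in this way does not have a guaranteed 5% level, because the feature that prompts the selection can be the feature that is then tested.

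Second, treatment cannot affect baseline, yet baseline is in the response. A time average taken over all three visits therefore mixes a visit with no effect into the estimate. A term that starts after baseline does not. The text allows either, and the two give different estimates and power for exactly the response pattern that selects this option. The baseline adjustment in E.11.b belongs to the per-visit regressions and is not carried into the mixed model.

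Adherence raises a related question, because it is unclear whether it has a baseline response. E.9.b says "We will construct medication possession ratios for antidepressants prescribed for the 3 months following enrollment and for 3-6 months following enrollment" and adds a self-report scale (MMAS-8). The E.10 row "Adherence with Antidepressant Medications (MPR* and BMQ)" is marked at baseline and names a different questionnaire. E.11.d uses "change in antidepressant adherence from baseline to 24 weeks".

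**Working it through.** **Inputs.** From E.13: 0.4 SD, two-sided alpha 0.05, 90% power, 20% dropout, 165 per arm. The documents give no within-person correlation, so ρ = 0.3/0.5/0.7 is assumed, equal between visits as a random intercept implies, with SD = 1.

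**1. The plan's own figure.** n = 2(1.960 + 1.282)²/0.4² = 131.3, so 132 per arm; 132/0.8 = 165 per arm, 330 in total. Power with 132 per arm is 90.1%. The stated figure reproduces.

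**2. Candidate contrasts.** For weights c on (baseline, week 12, week 24), SE = √(V × 2/132), with V as follows:

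| Contrast | Weights | V | Correlation with slope |
|---|---|---|---|
| Three-visit group main effect | (1, 1, 1)/3 | (1+2ρ)/3 | 0 |
| Common-baseline mean of weeks 12 and 24 | (−ρ, ½, ½) | (1−ρ)(1+2ρ)/2 | √(1+2ρ)/2 = 0.632/0.707/0.775 |
| Unconstrained group-by-post-baseline term | (−1, ½, ½) | 1.5(1−ρ) | √3/2 = 0.866 |
| Slope (baseline to week 24) | (−1, 0, 1) | 2(1−ρ) | 1 |

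**3. Ceiling on Type I error.** This is the chance under the null that either the time average or the slope reaches p < 0.05.
- Main effect or slope: 1 − 0.95² = 9.75%.
- Common-baseline mean or slope (bivariate normal): 8.6/8.3/8.0%.
- Unconstrained post-baseline term or slope: 7.3%.

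**4. Type I error under two possible triggers.**
- *Only the illustrated pattern triggers the slope* (intervention arm falls, usual care rises; simulated). With no common trend: 6.2% with the main effect as alternative, 5.5/5.4/5.3% with the common-baseline mean. With a common improvement of 0.4 SD: 5.0% for both. The highest value found was about 6.4%, at a common improvement of 0.1 SD.
- *A difference in change above 0.2 SD triggers the slope* (assumed threshold). The slope SE is 0.146/0.123/0.095, so the threshold is z = 1.37/1.62/2.10. The main effect is independent of the slope, so the error is P(slope chosen and significant) + P(slope not chosen) × 0.05:
  - ρ = 0.3: 0.050 + 0.830 × 0.05 = 0.092
  - ρ = 0.5: 0.050 + 0.896 × 0.05 = 0.095
  - ρ = 0.7: 0.036 + 0.964 × 0.05 = 0.084

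  With the common-baseline mean as alternative, simulation gives roughly 7% to 7.5%.

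**5. The missing treatment term.** Take a true effect of 0.4 SD at both follow-ups, that is (0, 0.4, 0.4), with 132 completers per arm:

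| Term fitted | Expected estimate | Power, ρ = 0.3/0.5/0.7 |
|---|---|---|
| Three-visit group main effect | (0+0.4+0.4)/3 = 0.267 SD | 84/76/68% |
| Unconstrained group-by-post-baseline | 0.400 SD | 89/96/99.8% |
| Common-baseline or baseline-adjusted week 12/24 mean | 0.400 SD | at least 99% |

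E.13's expectation of more than 90% holds for the main effect if 0.4 SD is itself the three-visit coefficient (99/98/95%). Under this pattern that would need 0.4 × 3/2 = 0.6 SD at each follow-up.

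**The case against.** The strongest defence is that the confirmatory comparison is fixed: week 24, with baseline as covariate. E.11.b also commits to unadjusted differences with confidence intervals and baseline-adjusted regressions at both follow-ups, so any diluted average would sit beside undiluted visit-specific estimates. That stands, and it limits the severity.

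The dilution is also conditional. No passage says that the time average is a three-visit main effect, and an effect described as immediate and lasting reads naturally as post-baseline. That stands too: the plan leaves the diluted model open but does not state it.

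Two stronger readings are tempting, and the documents do not support them.
- A reader might infer that the two gaps compound: usual care is likely to improve, so the illustrated pattern rarely occurs and an undefined time average is nearly always reported. But that pattern is only an example, and the stated criterion is any difference in trends. With the 0.2 SD trigger and a true effect of (0, 0.4, 0.4), the slope is chosen in 92/95/98% of trials. E.13's 65% of usual-care patients who might benefit from further treatment is not a mean change in score.
- A reader might infer that any term starting after baseline secures at least 99% power. The unconstrained term gives 89% at ρ = 0.3.

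On adherence, a baseline value could come from self-report, so the passages may be reconcilable; as written, they are not reconciled.

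**Conclusion.** The point holds for the longitudinal analysis only. The choice of comparison depends on outcomes by arm, and the rule is not stated, so the 5% level is not assured. The bound is 9.75%, 8.6/8.3/8.0% or 7.3%, according to the time average used. The realised error may be about 5% to 6%, if only the illustrated pattern triggers the slope, or about 7% to 9.5% under an assumed 0.2 SD trigger with the main effect or common-baseline mean as alternative.

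The undefined term is a separate gap. Its worst reading costs one third of a lasting effect and brings power below what E.13 expects; other permitted readings cost nothing in the estimate.

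The wording gaps are certain. The sizes rest on assumed correlations, compound symmetry and complete data in 132 patients per arm. The severity is minor to moderate.

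**What to change.** - Replace the graph-guided choice with one model fixed in advance: either weeks 12 and 24 as response with baseline as covariate, or all three visits with a common baseline mean across arms. Include treatment-by-visit terms in either case.
- Name one contrast: the mean of weeks 12 and 24, or week 24.
- Keep the plots as description and label the slope model exploratory.
- State in E.13 which visits the time-averaged difference covers.
- Apply the same model to E.11.c outcomes that have a baseline value. For adherence, reconcile E.9.b (possession ratios only after enrolment, plus a self-report scale) with E.10 and E.11.d, which imply a baseline value, and settle which questionnaire is meant.

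The cost is a few lines of SAP text and standard code, with no new data or patients. What is lost is the freedom to choose the contrast after seeing the data, and that loss is small. If the effect instead grows linearly, (0, 0.2, 0.4), the common-baseline mean of weeks 12 and 24 is (0.2 + 0.4)/2 = 0.30 SD, with 90/93/98% power against 78/90/99% for the slope.

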E.11.a Analyses of Success of Randomization: We will first determine the success of the randomization process for potential prognostic factors that may affect the primary outcomes of severity of depressive symptoms and functional status, but were not considered in minimization scheme. These factors include variables such as prior hospitalization or baseline severity of anxiety symptoms. Potential differences between groups will be determined through the use of t-tests or chi-square analyses, as appropriate. When there are significant differences in the distribution of these variables, they will be included as covariates in multivariable analyses. The interpretations of final results will also be made carefully in the presence of significant baseline differences.

E.11.b Analyses Relevant to Primary Aims: Primary study analyses will determine the effectiveness of the PS-cCBT intervention in decreasing depressive symptoms (IDS-SR), improving functioning and quality of life (VR-12, Q-LESQ-SF), and increasing recovery focus (RAS) at 24 weeks post-enrollment. We will also examine the impact of the intervention on depression coping efficacy and skills, antidepressant adherence, and initiation and completion of traditional in-person psychotherapy (contingent on symptoms).

Analyses will be of two broad types, those that assess intervention effects at each assessment point (12 weeks and 24 weeks), and those that determine effects over time. Primary analysis will be based on “intent to treat” principle, with all randomized patients included in the originally randomized group, regardless of whether they have subsequently dropped from their assigned treatment group.

Univariate Analyses: In the first phase of analysis (data verification), we will examine the distribution of all study variables to assess extreme values, missing data, variances, possible coding errors, skewness and whether or how to categorize skewed data. We will then describe means ($\pm SD$) for the continuous IDS-SR, VR-12, Q-LESQ-SF, and RAS measures by study group for each assessment time for the entire sample and

for each of the study sites, separately.

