We propose to enroll 330 patients in total (165 per group). The sample size was calculated to provide 90% power to detect a difference in levels of depressive symptoms at the primary end-point of 24 weeks, conservatively assuming a mean effect size of 0.4 SD with a two-tailed alpha of .05 and 20% dropout. We expect that this effect size is conservative based on the meta-analysis completed by Spek et. al. The meta analysis of cCBT interventions for depression and anxiety found that RCTs of cCBTs for depression and anxiety with therapist support had a mean effect size of 1.00 SD, while unsupported cCBT had a mean effect size of 0.26 SD. This suggests that we can reasonably expect our peer-supported cCBT to have an effect size in the range of 0.4 to 0.6 SD compared with enhanced usual care. In another study, Titov et al, reported an effect size of 1.1 from a technician supported cCBT for depression. In our pilot work, congruent with reported effect sizes in the literature in other populations, we found that depressive symptoms among Veterans with depression enrolled in BTB were reduced by 27%, with a mean BDI-II of 21.9 (SD=11.1) at baseline and 16 (SD=13.5) at 8 weeks. Although the pilot study did not have a control group and the endpoint was at 8 weeks, the effect size estimated based on changes from baseline to 8 weeks can be considered to range from 0.43 SD (with an assumed SD of 13.5) to 0.53 SD (an assumed SD of 11.1). Thus, based on the meta-analyses and our pilot data, we consider a between-group difference of 0.4 SD a clinically meaningful and detectable effect size for the proposed intervention. We also note that for the analysis using longitudinally measured data, the power will also depend on the within-person correlation. The proposed sample size, however, will likely give greater power than 90% if 0.4 SD is the time-averaged between-group difference.

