For the secondary outcome of rate of initiation of a traditional psychotherapy, assuming that at 12 weeks, 50% and 65% of patients in the PS-cCBT and the enhanced usual care groups, respectively, could benefit from more intensive intervention and further conservatively assuming that 20% will drop out by 12 weeks, we expect the proposed number of enrollees with less than full response will be approximately 66 in the PS-cCBT group and 86 in enhanced usual care group. With these expected numbers of patients in need of more intensive treatment at 12 weeks, we will have 63% power to detect the difference of 55% initiating a traditional therapy in PS-cCBT group vs. 35% initiating a traditional therapy in the enhanced usual care group, and 80% power to detect the difference of 59% initiating a traditional therapy in PS-cCBT group vs. 35% base rate.

F. DISSEMINATION/IMPLEMENTATION

We will disseminate the results of this project through usual channels such as journal publication and presentations at conferences. [name] has regular contact with members of the VA Mental Health QUERI and both Drs. [name] and [name] are part of the QUERI Recovery – Peer Support working group. Drs. [name] and [name] regularly apprise this group of team progress in peer related research. One of the operational letters of support comes from [name] [name], the National Director of Peer Support Services. He also regularly attends the QUERI-Peer Support working group calls and will receive regular updates throughout the course of the trial.

[name] and [name] have offices that are co-located with the Primary Care-Mental Health Integration (PC-MHI) implementation and the PC-MHI evaluation team. Thus, they have regular contact with Drs. [name] and [name] who lead and evaluate efforts to improve integration of mental health services into primary care settings, respectively. This proposal has been discussed with [name] who wrote an operational letter of support and gave several suggestions regarding how to make this proposal relevant to primary care services in the VHA.

Team members also regularly communicate with both the VHA Office of Mental Health Operations and VHA Office of Mental Health Services. If we find that the intervention leads to improved outcomes, we will seek partnerships to explore how the intervention can be more widely implemented throughout the VA.

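### Psychotherapy initiation is compared only among patients still symptomatic at week 12, so on its own the comparison does not support a claim that PS-cCBT increases initiation

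*Combined protocol and SAP*

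**What the plan says.** E.11.c restricts the logistic regression for psychotherapy initiation to patients "who have continued significant depressive symptoms at 12 weeks, defined as IDS-SR >16". It concedes that the patients so selected are likely to differ between arms, and answers that "the model will be adjusted for variables that show meaningful differences between groups at 12 weeks". It names the main interest as whether PS-cCBT raises the likelihood of starting traditional therapy.

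E.13 sizes this comparison by "assuming that at 12 weeks, 50% and 65% of patients in the PS-cCBT and the enhanced usual care groups, respectively", could benefit from more intensive treatment. With 20% dropout that gives about 66 and 86 patients. Power is stated as 63% for "55% initiating a traditional therapy in PS-cCBT group vs. 35% initiating a traditional therapy", and as 80% for 59% vs 35%.

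E.11.b states the intent-to-treat rule, "with all randomized patients included in the originally randomized group", for the primary analysis, and describes the psychotherapy outcome as contingent on symptoms. E.9.b builds yes/no psychotherapy indicators from the records of all enrolled patients. No comparison of initiation in all randomised patients is specified, and no sensitivity analysis for the selection.

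**The concern.** IDS-SR is a primary outcome that PS-cCBT is meant to lower. If it does, the patients above 16 at week 12 are a different selection in each arm. PS-cCBT patients who remain symptomatic may be more severely or persistently ill than their EUC counterparts, and such patients may be more or less inclined to start therapy.

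Adjustment does not restore the lost balance. If the adjusters are measured at week 12, some may be effects of treatment, and conditioning on them can remove part of a real effect. If they are baseline variables that happen to differ within the subset, unmeasured differences remain. Either way the covariate set is chosen from the data.

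At stake is a sentence in the trial report saying that PS-cCBT leads more Veterans into in-person therapy, when the randomised arms as a whole may differ little or not at all in how many started.

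**Working it through.** **Inputs.** E.13: "We propose to enroll 330 patients in total (165 per group"); "further conservatively assuming that 20% will drop out by 12 weeks"; 50% and 65% still in need; initiation 55% or 59% vs 35%. Two-sided alpha of 0.05 is stated in E.13 for the primary endpoint and is assumed here.

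**1. The plan's own figures.**
- Subset sizes: 165 × 0.8 × 0.50 = 66; 165 × 0.8 × 0.65 = 85.8, about 86.
- Power = Φ[(d − c − 1.96·SE0)/SE1], with continuity correction c = ½(1/66 + 1/86) = 0.0134.
- 55% vs 35%: pooled rate (36.3 + 30.1)/152 = 0.437, SE0 = 0.0812, SE1 = 0.0800. (0.20 − 0.0134 − 0.1591)/0.0800 = 0.344, so power is 63.5%.
- 59% vs 35%: SE0 = 0.0815, SE1 = 0.0794, power 80.0%.

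Both stated values reproduce. The arithmetic is sound; the question is what the contrast means.

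**2. Selection alone, with no effect on initiation in anyone.** Assume a latent severity trait correlated 0.3 to 0.7 with week-12 symptoms, cut-offs giving 50% and 65% symptomatic, 35% initiation in the EUC subset, and an odds ratio per SD of the trait for initiation. A simulation of 2,000,000 draws gives:

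| Odds ratio per SD | Spurious subset difference (points) |
|---|---|
| 2 to 3 (sicker patients initiate more) | +1.0 to +3.4 |
| 1/2 to 1/3 (sicker patients initiate less) | −1.0 to −3.5 |

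The two-sided false-positive rate at 66 vs 86 is about 5.2% to 7.3%. Stronger assumed links (correlation up to 0.9, log-odds −1 to 1.5 per SD) widen the range to about −4 to +6 points.

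**3. From the subset to all patients with 12-week data (132 per arm).** Let r be the initiation rate among patients at or below the cut-off, assumed equal in both arms. The plan gives no value for r. PS-cCBT: 0.50 × 0.55 + 0.50·r. EUC: 0.65 × 0.35 + 0.35·r.

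| r | PS-cCBT | EUC | Difference (points) | Power |
|---|---|---|---|---|
| 0% | 27.5% | 22.75% | 4.75 | 14% |
| 5% | 30.0% | 24.5% | 5.5 | 17% |
| 10% | 32.5% | 26.25% | 6.25 | 20% |
| 20% | 37.5% | 29.75% | 7.75 | 27% |

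Power here is without continuity correction. For r = 0: (0.0475 − 1.96 × 0.0534)/0.0533 = −1.07, which gives 14%.

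**4. Break-even.** With r = 0, overall initiation is equal when the PS-cCBT subset rate is 0.65 × 0.35/0.50 = 45.5%, because 0.50 × 45.5% = 22.75%. At 45.5% vs 35% the planned subset test would favour PS-cCBT in about 26% of trials (21% with continuity correction), although the same number of Veterans started therapy in each arm.

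**5. Bounds for patients who would be symptomatic under either assignment.** Assume PS-cCBT never worsens week-12 status. These patients are then 0.50/0.65 = 76.9% of symptomatic EUC patients. Their EUC initiation rate lies between (0.35 − 0.231)/0.769 = 15.5% and 0.35/0.769 = 45.5%. At 55% in PS-cCBT the effect lies between +9.5 and +39.5 points. The standard error of the lower bound is √(0.55 × 0.45/66 + 1.3² × 0.35 × 0.65/86) = 0.091, so z is about 1.05 (about 1.5 at 59%), and zero is not excluded. Without that assumption, the bounds run from −13 to +69 points if 40% are symptomatic under either arm.

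**The case against.** The strongest reply is that the subset question is legitimate. E.8.a says patients with continuing problems will be encouraged towards more intensive treatment, so initiation among those still in need is what the investigators want to know, and they say openly that the outcome is contingent on symptoms. E.11.c admits that the groups will differ. Against 20 to 24 points, a selection shift of a few points is a caveat. An all-randomised comparison answers a different question, diluted because PS-cCBT leaves fewer patients in need, and has little power.

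Much of this stands, and it rules out several stronger readings:
- A reader might infer that selection inflates the result. The documents give no direction; the sign depends on whether sicker patients initiate more or less.
- A reader might infer that the model adjusts for mediators such as coping or hope. E.11.c names no variables, and the covariate list in E.11.b is essentially pre-treatment. The fair criticism is that the wording allows week-12 variables and leaves the set open.
- A reader might infer a breach of intent to treat. E.11.b states that rule for the primary analysis only.
- A reader might take 4.75 points as the corrected value of 20. It is a different quantity and rests on an assumption about patients at or below the cut-off.

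The reply does not justify the causal wording. Acknowledging that the groups differ, then adjusting for whatever differs at 12 weeks, does not make the comparison a randomised one.

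**Conclusion.** The concern holds in a limited form. The initiation comparison is made in a set defined by a post-randomisation outcome that the plan expects treatment to change, with an adjustment set that is unspecified and may include treatment-affected variables. As planned and on its own, it does not support the conclusion that PS-cCBT increases initiation.

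It would go too far to say the comparison can show nothing. Null selection bias is about 1 to 3.5 points either way under the stated latent-trait assumptions, and a large difference with explicit assumptions could support a bounded claim. At 66 vs 86 patients and the planned rates, however, the bounds do not exclude zero. The more consequential point is interpretive: a 20-point subset difference corresponds to 4.75 points overall if no one else initiates, or 5.5 to 7.75 points if 5% to 20% of the others do. This is a secondary outcome; the primary outcomes and the stated power figures are unaffected.

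**What to change.** 1. Add a comparison of in-person psychotherapy initiation by 24 weeks in all randomised patients, by logistic regression with site and the minimisation factors (age group, gender, prior antidepressant fill, PHQ-9 severity), using the indicators already built under E.9.b. Base any statement that PS-cCBT increases initiation on it. State one time window: E.11.c describes both a 12-to-24-week period and initiation by week 24, which leaves early starters unclear. Counting from randomisation settles this, but also brings in the 12-week treatment period.
2. Keep the IDS-SR >16 comparison as supportive. Adjust only for prespecified baseline variables, describe it as conditional on week-12 symptoms, and add a bounds or principal-stratum sensitivity analysis.
3. If symptom status by initiation is tabulated by arm, keep it descriptive. Testing unmet need (symptomatic and no therapy started) is tempting but is not evidence on initiation. With 35% initiation in both subsets it is 0.50 × 0.65 = 32.5% vs 0.65 × 0.65 = 42.25%, and at 132 per arm the test rejects in about 37% of trials on symptom response alone.

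The cost is SAP wording, one extra model and one sensitivity analysis, with no new data collection. The drawback is low power: about 14% at 27.5% vs 22.75% with 132 per arm. The all-randomised result should be presented mainly as an estimate with its confidence interval.
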